8.2 Statistical methods

Biostatistician, Co-I [name], will be responsible for coordinating data management and statistical design/analyses aspects required for feasibility studies including data cleaning, analytical set construction, documentation, analyses, and preparation of data summaries for reporting purposes. He will provide leadership in designing/formatting data collection forms to reduce data collection/recording errors and develop a well-defined/comprehensive data quality assurance program to ensure complete, accurate, and valid data, while limiting variability in data collection/recording. Study data will be managed using REDCap (Research Electronic Data Capture), is a secure web application designed to support data capture for research studies, providing user-friendly web-based case reports, real-time data entry validation (data types/range checks) audit trails, and a de-identified data export mechanism to statistical packages (SPSS, SAS, Stata, R/S-Plus). **Analysis Plan.** Study 2 is to establish feasibility; descriptive statistics, including means/standard deviations (continuous variables) and frequencies (categorical variables) will be used to characterize the data. Study 2 will provide estimates for the primary endpoint (GWG) to power a future RCT. Linear mixed-effects models will be used to assess differences between intervention and control groups with respect to changes in continuous outcomes over time (from pre- to post-intervention; daily/weekly) on GWG and related health outcomes. Generalized estimating equations with a logit link will be used to assess differences between intervention and control groups for dichotomous outcomes over time. Because this is a

pilot study, the primary focus of these analyses is for parameter estimation; any hypothesis test will be interpreted with extreme caution to guide the future RCT as this pilot study is deliberately not powered to make definitive claims. All modeling development and simulation will be done in Matlab with SIMULINK and the use of functional data analysis modeling for time-varying modeling will rely on SAS. **Participant Dropout & Other Missing Data.** While every attempt will be made to collect complete data and prevent participant dropout, missing data are inevitable. We have inflated the sample size for Study 2 as described above. We will compare characteristics of those with missing data to those with complete data. These feasibility studies will provide valuable information to minimize missing data in the future RCT (e.g., they will help determine reasons for drop-out, assess which methods for data collection need to be modified/changed, examine data collection and retention of the control group, etc).

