1.3 Secondary Study Endpoints

Healthy eating [HE] and physical activity [PA] behaviors

Self-regulation behaviors

Sleep behaviors

Adult temperament

Psychological well-being (body image satisfaction, depressive symptoms, anxiety, perceived and actual stress)

Motivational determinants of HE and PA (attitude, social norm, perceived control, self-efficacy, intention)

Social-demographic and health correlates (e.g., age, pregnancy history, etc.)

Fetal growth, weight, height, birth weight, postnatal weight

Mobile resting metabolic rate, basal metabolic rate, metabolism

R56:

C-reactive protein/micronutrients (e.g., folate)

Maternal and infant labor and delivery complications

Maternal/Fetal hydration

Maternal/Fetal medical record data

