8.0 Statistical Plan

8.1 Sample size determination

For Study 2, Julios⁵⁰ effectively argues a sample size of 12 per group is adequate to assess feasibility, address regulatory considerations, and obtain sufficient precision of the mean and variance to perform a formal sample size and power calculation for the future RCT. The primary endpoint of the future RCT will be powered on GWG. Factoring in an anticipated 20% subject drop-out based on our pilot work,⁵⁰⁻⁵² we will recruit a total of 30 subjects (i.e., 15 per group).

48. Symons Downs, D. (2011). Determinants and outcomes of physical activity in pregnancy: Findings from Active MOMS, a randomized physical activity intervention for pregnant women. *Annals of Behavioral Medicine*, 41, S135.
50. Julios, S. A. (2005). Sample size of 12 per group rule of thumb for a pilot study. *Pharmaceutical Statistics*, 4, 287-291.

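### With 24 to 30 women, the logit GEE in section 8.2 needs a small-sample variance and an empty-cell rule, and one-time dichotomous outcomes need a stated group comparison

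*Combined protocol and SAP*

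**What the plan says.** For group comparisons of binary data, section 8.2 has one sentence: "Generalized estimating equations with a logit link will be used to assess differences between intervention and control groups for dichotomous outcomes over time". It does not name a covariance estimator, working correlation, reference distribution, small-sample correction, or a rule for a cell with no events. Section 8.2 also plans descriptive work, in which "frequencies (categorical variables) will be used to characterize the data".

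Section 8.1 accepts that "a sample size of 12 per group is adequate to assess feasibility" and inflates this: "Factoring in an anticipated 20% subject drop-out based on our pilot work", giving 15 per group and 30 in total. On purpose, section 8.2 says that "the primary focus of these analyses is for parameter estimation" and that "this pilot study is deliberately not powered to make definitive claims".

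Two kinds of dichotomous outcome appear. Some are repeated: Appendix A turns the CES-D into case status at a cut-off of 16, and Appendix B schedules it pre-intervention, monthly and post-intervention. Others occur once per pregnancy: section 1.3 lists "Maternal and infant labor and delivery complications", and section 6.2 takes gestational diabetes from the medical record. No event rate is given for any of them.

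**The concern.** The GEE sandwich variance is justified by a large number of independent clusters. Here the clusters are women, 24 to 30 in all, and at that size the uncorrected sandwich tends to be too small. Separately, a logit contrast has no finite value when a group, or a group at one time point, has no events or only events. Software does not always stop in that case; it may print a very large coefficient with a standard error that means nothing.

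These analyses are meant to supply estimates. An interval that is too short, or an estimate that does not exist but is printed as though it did, damages that product directly. The promise to read tests cautiously does not mend the interval.

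**Working it through.** **1. The plan's own figure.** 12 / (1 - 0.20) = 15 per group, 30 in total. It reproduces. The checks use n = 12 and n = 15. The non-randomised normal-weight controls in section 16.2 are left out.

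**2. Assumed inputs (none are in the documents).** Prevalence 5-50%, equal in both arms unless stated; 2, 6 or 7 occasions; within-woman correlation as given; two-sided 95% level.

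**3. One-time outcome: chance that at least one arm has no events or only events.** 1 - (1 - [(1-p)^n + p^n])^2.
- p = 0.10, n = 12: 0.9^12 = 0.282; 1 - 0.718^2 = 48%. n = 15: 0.9^15 = 0.206; 1 - 0.794^2 = 37%.
- p = 0.20: 13% (n = 12), 7% (n = 15). p = 0.30: 3%, 1%. p = 0.05: 79%, 71%.
- 10% v 5%, n = 12: 1 - (1 - 0.282)(1 - 0.540) = 67%; n = 15: 57%.

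**4. Pre/post group-by-time.** Four group-by-time cells must all be neither empty nor full. If the two occasions were independent, the failure chance would be 1 - (1 - [(1-p)^n + p^n])^4:
- p = 0.10: 1 - 0.718^4 = 73% (n = 12); 1 - 0.794^4 = 60% (n = 15).
- p = 0.20: 1 - 0.931^4 = 25%; 1 - 0.965^4 = 13%.

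Positive correlation within a woman lowers this slightly. Simulation with latent correlation 0.5 gave 71% and 60% at p = 0.10, and 22% and 13% at p = 0.20. Over the settings tried, the ranges were about 58-72% and 13-22%.

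**5. Outcomes measured many times.** Simulated under no group effect: six occasions, latent correlation 0.5, independence working correlation, 2,000 runs per setting (Monte Carlo error about 0.5 points). Coverage of the nominal 95% interval for group-by-time, among finite fits:

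| Prevalence | n | Uncorrected sandwich, z | Mancl-DeRouen, t |
|---|---|---|---|
| 0.1 | 12 | 82.7% | 86.7% |
| 0.1 | 15 | 87.5% | 91.5% |
| 0.2 | 12 | 91.9% | 94.6% |
| 0.2 | 15 | 91.4% | 93.8% |
| 0.3 | 12 | 91.8% | 95.6% |
| 0.3 | 15 | 92.9% | 95.2% |
| 0.5 | 12 | 91.6% | 95.7% |
| 0.5 | 15 | 92.5% | 95.5% |

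For the group main effect, uncorrected coverage was 91.9-94.3%.

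With seven visits, ICC 0.3 and exchangeable GEE, rejection by the uncorrected sandwich was about 6-9% at 20-40% prevalence and up to about 13% for group-by-time at 10%. Mancl-DeRouen with t brought it to about 4-6% at 20-40%. The table's non-coverage at 10% (100 - 82.7 = 17.3%, and 100 - 87.5 = 12.5%) shows how far this worst case moves with the assumed correlation and visit count.

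**6. Few occasions, finite fits only.** Single occasion, exact enumeration: logit Wald coverage is 94-98% at p = 0.3-0.5 and 99-100% at p of 0.2 or less. Pre/post group-by-time: 92.9-95.0% at p = 0.3-0.5 and 95.6-98.5% at p = 0.1-0.2.

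**7. What a separated fit looks like in output.** Pre/post, 12 per arm, p = 0.20, ICC 0.3, 600 trials: in 456 with no empty cell, 3.3% rejected. In 87 more, a cell was empty but software still returned an estimate; 92% of these had a coefficient beyond 8 in absolute value, and 40% rejected.

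**The case against.** **It is a pilot, and the key endpoint is not touched.** This stands, and it limits the weight of the point. Gestational weight gain is continuous, is analysed by mixed models, and is what the future trial will be powered on. No dichotomous outcome is primary.

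**The plan does not say it will use the uncorrected sandwich.** This also stands. A corrected variance is compatible with the text. The short intervals follow from the usual software default; what the document itself shows is that the choice is left open.

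**Delivery complications are not assigned to GEE.** Correct: the sentence covers outcomes followed over time. A reader might infer that the plan applies an unsuitable method to one-time complications, or that GEE is its only treatment of binary data. Neither is supported, because frequencies are planned as well. The gap for one-time outcomes is that no between-group method is stated.

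**Intervals are not too narrow in general.** A reader might infer that all dichotomous intervals will be short, and a pre/post simulation that counts every returned fit seems to agree: (0.033 x 456 + 0.40 x 87) / 543 = 9.2% rejection. That excess comes from divergent empty-cell fits. Among finite fits, single-occasion and pre/post intervals for uncommon events are near nominal or too wide.

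**The rates are assumed.** True, and the problem fades as outcomes become common: at 30% the empty-arm chance for a one-time outcome is 3% or 1%.

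**Conclusion.** The point holds in a limited form and is worth correcting. It has three parts.

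- **Repeated outcomes:** under the default variance, intervals are modestly short at 20-50% prevalence and clearly short for group-by-time near 10%.
- **Sparse cells:** at about 10% prevalence, a pre/post group-by-time contrast would more often than not have no finite value, and the plan has no rule to stop a divergent fit being reported as a result.
- **One-time outcomes:** no comparison is stated, and the obvious logit contrast would fail in roughly a third to a half of trials at 10% in both arms.

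The sizes rest on assumed prevalences, visit counts and correlations, and the first part also on the default sandwich with z quantiles. The claim of short intervals does not extend to single-occasion or pre/post analyses of uncommon events. The point goes beyond missing detail because the named method, run at its defaults, gives poorer intervals or none for the estimation that section 8.2 puts first.

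**What to change.** Add two provisions to section 8.2.

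1. For repeated dichotomous outcomes, keep logit GEE but use a bias-corrected sandwich variance (for example Mancl-DeRouen) with t quantiles based on the number of women.
2. For one-time or sparse outcomes, and whenever a group-by-time cell is empty or full, report counts and the risk difference with a score interval (Newcombe or Miettinen-Nurminen). Use Firth-penalised logistic regression if an odds ratio is wanted. Do not report a separated GEE fit.

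The cost is a few sentences and slightly wider intervals for repeated outcomes. The corrected variance does not cure empty cells and does not fully restore coverage for group-by-time at 10% prevalence (86.7% and 91.5% in the table), so the second provision is needed alongside the first.

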9.0 Confidentiality, Privacy and Data Management

9.1 Confidentiality

Data will be secured using password protected computer files, locked file cabinets for hard copy data, locked offices and laboratory space within locked facilities (Rec Hall for the Exercise Psychology Laboratory and Noll Laboratory where the intervention will be delivered). Subject data will also be coded with participant IDs for coding purposes. Data will be entered and stored in the secure REDcap system. Ultrasound scan data and biological specimens will be identified by participant ID # only and will not include any personal identifiers. The same participant ID #'s will be used for these data as for the parent Healthy Mom Zone study. A master list linking participant identifying information and participant ID #'s will be stored in a locked, secure location. Only authorized personnel listed on the protocol will have access to data and specimens.

9.1.1 Identifiers associated with data and/or specimens

Identifiers will include name, home address, telephone number, email address, medical record data.

9.1.1.1 Use of Codes, Master List

A list containing a code associating the identified data with the participant ID will be stored in the secure Redcap system. Access to the identified data will be limited to project staff who will need to understand this information for contact and tracking purposes (reminder calls, repeated data collection, etc.) which will include:

The PI, [name]

Project Coordinator, [name] who will be directly working with the scheduling of participants, reminders and Redcap

Project Staff Member [name] who will also be working with the scheduling of participants, reminders, and Redcap

This list will be destroyed for 5 years after the study has been completed per American Psychological Association guidelines.

9.1.2 Storage of Data and/or Specimens

Electronic data will be stored in the secure Redcap system. Hard copy of data will be stored in locked file cabinets in locked laboratory space. Data will be saved for 5 years after the study has been completed per American Psychological Association guidelines. This study will be issued a Certificate of Confidentiality. Researchers will not disclose or provide any identifiable information without the subject's prior consent or where permitted according to NIH's Policy on Issuing Certificates of Confidentiality.

9.1.3 Access to Data and/or Specimens

Access to the data will have different levels in the Redcap system. As noted above, the PI [name], [name], and [name] will have access to fully identified data. The other collaborators and research assistants will have access to deidentified data. Non-PSU study team members will be made aware they are also subject to the disclosure restrictions according to NIH's Policy on Issuing Certificates of Confidentiality.

9.1.4 Transferring Data and/or Specimens

De-identified electronic data will be shared with the PSU collaborators and [name] at Arizona State University via the secure Redcap system. The researchers do not plan to release identifiable information collected in the study. However, if researchers consider releasing identifiable information in the future – the individual or institution receiving the identifiable information will be made aware they are also subject to the requirements of subsection 301(d) of the Public Health Service Act.

9.2 Privacy

We will take all possible steps to ensure confidentiality. Subjects will be continually ensured through the consent process, data collection procedures, and intervention sessions that they are not obligated to participate in this study and that their answers will be held with strict confidentiality. We will be using the secure system of Redcap for data entry, collection, storage, and management. The security of the research project data will be maintained through network hardware and user authentication (usernames and passwords). Access to Redcap will be restricted. Back-ups of the project data files will occur every night, with user data backed-up incrementally Monday through Thursday and complete back-ups every Friday. Archival back-ups, stored indefinitely, are cut on the last weekend of every month. Section 9.1.3. illustrates who will have access to which levels of data in Redcap.

As far as privacy for the subjects, they will complete a consent form for participation which explains the study. HIPAA authorization will be obtained from subjects in order for us to have access to their medical record data to obtain their prenatal record (e.g., gestational weight gain, complications, etc) and labor/delivery data. A subject can choose to not allow us to have access – and she can decide to provide the health information she wants to share.

Steps to protect subject privacy and privacy interest include using Subject ID codes, limiting the access to identified data, conducting the intervention in a closed-door facility with limited traffic and access, not disclosing who is participating in the study in any public fashion (never identifying individual subjects in research presentations, discussions, etc.), using the secure Redcap system for subjects to enter their data and not answering study questions out loud in public places or laboratory spaces with others present, and conducting the physical assessments in the CRC.

10.0 Data and Safety Monitoring Plan

This research does not involve more than minimal risk to the subjects. However, because this is a federally-funded study, a DSMP was required by the granting agency and therefore, we have a DSMP. This research involves minimal risk to the subjects as defined in SOP HRP-001 "Minimal Risk is the probability and magnitude of harm or discomfort anticipated in the research that are not greater in and of themselves than those ordinarily encountered in daily life or during the performance of routine physical or psychological examinations or tests."

10.1 Periodic evaluation of data

Daily weight data will be collected for intervention monitoring. Weekly HE and PA behaviors, self-regulation, psychological well-being, motivational determinants of HE and PA, and weight behaviors will also be collected and used to inform the intervention counseling in the following week. Also, as described above, will also collect PA session data on symptoms monitoring at pre-exercise, 5-min, 15-min, 25-min, and post-exercise.

See attached protocol for unexpected or adverse events monitoring.

10.2 Data that are reviewed

Definition of adverse event. An adverse event shall be defined as any detrimental change in the participant's condition, whether it is related to study interventions, study outcomes, or to another unrelated illness.

Adverse events unrelated to the study interventions. Adverse events due to illnesses unrelated to study interventions may be grounds for withdrawal if the illness is considered significant by the study investigators or if the participant is no longer able to effectively participate in the study. A significant illness would be one that would compromise the women's ability to function normally and thrive such as the diagnosis of a disease requiring ongoing and intensive treatment and/or one requiring repeated hospitalizations or physician visits. Subjects experiencing routine, minor, self-limited acute illnesses that typically occur during pregnancy and do not affect long-term growth will not be recorded, and the women will continue to participate in the study. Examples of minor illnesses include bronchiolitis, upper respiratory infections, and urinary tract infections. Examples of minor unanticipated events from the PA session may be minor aches, a cold, feeling uncomfortable, mild nausea. Medications for acute, self-limited illnesses such as those stated above will not be recorded, but chronic medication use (≥ 1 month) will be recorded. Further surgical conditions that could impact HE, PA and GWG will be recorded and if the participant's physician determines that these conditions can affect prenatal weight gain, the participant will be withdrawn from the study.

Documentation of an AE unrelated to the study interventions that are not considered minor illnesses and those that can significantly affect the baby will be recorded on the AE form and reported to the IRB. See the protocol for unexpected or adverse events for actions and reporting of the unexpected events and AEs.

Adverse events potentially related to the study interventions. While the majority of OW/OBPW have excessive GWG (over the threshold ranges for prepregnancy weight category as illustrated in the table below:

Institute of Medicine Weight Gain Recommendations for Pregnancy

Prepregnancy Weight Category	Body Mass Index*	Recommended Range of Total Weight (lb)	Recommended Rates of Weight Gain† in the
			Second and Third Trimesters (lb)
Underweight	Less than 18.5	28–40	1 (1–1.3)
Normal Weight	18.5–24.9	25–35	1 (0.8–1)
Overweight	25–29.9	15–25	0.6 (0.5–0.7)
Obese (includes all classes)	30 and greater	11–20	0.5 (0.4–0.6)

*Body mass index is calculated as weight in kilograms divided by height in meters squared or as weight in pounds multiplied by 703 divided by height in inches.

†Calculations assume a 1.1–4.4 lb weight gain in the first trimester.

Modified from Institute of Medicine (US). Weight gain during pregnancy: reexamining the guidelines. Washington, DC. National Academies Press; 2009. ©2009 National Academy of Sciences.

It is theoretically possible that behavioral interventions designed to manage GWG in OW/OBPW could result in energy imbalance and insufficient weight gain. The pilot studies that serve as the foundation for the current study **did not** find an association between study interventions and these adverse events. However, we will be monitoring weight on a daily basis and examining GWG on a weekly basis and will consult with co-investigator, [name], OBGYN to identify

if a woman has insufficient weight gain for gestational week. Indicators of insufficient weight gain are, for example, weight loss of >3% in a week, or 0% weight gain in a 4-week cycle. OW/OPBW should gain, on average, .5 lb per week, so we will use this as a threshold to understand the context of the weekly GWG relative to her overall GWG and clinical insight. We will consult with the participants OBGYN provider and [name] to determine if the participant should be removed from the study for insufficient GWG.

The study's informed consent document will include information indicating that the study team will communicate with the participant's OBGYN or Primary Care Provider. The study team will ensure that open lines of communication exist with the healthcare provider in addition to the weight monitoring and review. To establish the lines of communication between the study team and the PCPs, upon participant randomization, the participant is required to have a physician consent form completed to "clear her" for study participation. Healthcare providers will also be directly notified about their patient's participation in the study. A brief description of the study will be shared with them as well as a contact number to call the study team should the provider become concerned about insufficient GWG by their patient. Recognizing that weight monitoring is typically performed at all regularly scheduled primary care appointments, we will ask providers for their collaboration in monitoring prenatal weight gain in that we would like to be alerted to any concerns that their patient is demonstrating insufficient weight gain.

During each face to face visit, staff will calculate weight, BMI, and weight change. If the adverse risk for inadequate weight is identified, we will modify treatment (i.e., recommending increased energy intake). The PIs will review weight and applet data at least twice monthly and then contact the healthcare providers and co-investigator, [name] when appropriate after each individual is closely evaluated as described below. For any individual who meets initial screening criteria for weight gain concerns, numerous factors will be considered in determining whether the women's weight gain is problematic and/or related to study interventions. Examples of such factors include nausea, vomiting, and interval illness. If either the healthcare provider or the study investigators believe that it is possible that these growth patterns are a negative result from study participation, the women will be withdrawn from the study.

Co-Investigator, [name], our biostatistician, will include protocol compliance with inclusion and exclusion criteria, participant compliance with the interventions, and adverse events in consultation with the PI [name], Co-I, [name], and study staff ([name], [name]).

